#### Risks and adverse effects

There are no risks or adverse effects from the OCT mapping procedure or lesion measurement procedure.

The OCT scanner is a CE marked device using a low power, eye-safe, Class I laser for the scanning process. The scan does not expose the patient to any unsafe optical radiation.

For this study, the CE-marked OCT scanner has been modified by the addition of a non CE-marked prototype Marking Accessory ('Marker'). This Marker produces a small dot of ink on the subject's skin at the centre of the OCT scan when a trigger is depressed by the operator. The ink is approved for use in surgical markers. The Marker contacts the skin but is cleaned between each patient using disinfectant wipes. After mapping and before surgery the patient's skin is prepared in the normal manner, so there is no risk of infection. As the Marker is not CE-marked, MHRA approval of its use is being obtained.

#### Data and Analysis

The following data and analysis will be performed:

##### 1. Primary Objective

- The average number of MMS stages will be calculated for each arm by dividing the total number of MMS stages for all the patients in the arm, by the number of patients in the arm. The 95% confidence levels for each arm will be calculated.

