## Objectives:

Primary Objective:

- Show that the average number of MMS stages by using pre-surgical margin mapping with OCT is  $< 1.4$

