#### Study Design:

Interventional Randomised Controlled Trial (RCT)

Previously published research [1-5] has shown that, under controlled conditions, OCT mapping of BCC margins is more accurate than clinical assessment and so is expected to produce a reduction in the number of MMS stages. However, the efficiency of the technique, in terms of the reduction in MMS stages versus the additional time required to OCT map the lesion, has not been quantified.

This RCT is designed to quantify the improvement in efficiency, and validate that it is more efficient than standard MMS. The study comprises two Arms, one is the OCT arm and one is the Control Arm. In the OCT Arm, OCT is used to map the tumour margins and the resulting number of MMS stages is recorded.

In the Control Arm, standard MMS is performed.

In order to be completely sure that the reduction in MMS stages using OCT has not been obtained at the cost of increasing the amount of tissue excised, all tumours are also mapped at initial consultation, prior to randomization, by a second observer. See Figure 1 Outline Protocol below.

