#### Figure 1. Outline Protocol

##### Initial Steps

1. Informed consent is obtained from eligible patients
2. Observer #1 (not the surgeon) maps the extent of the BCC tumour using OCT. The time taken, size and shape of the mapped border is recorded.
3. The OCT marks are removed and the patient is asked to return at a later date for the surgical procedure
4. Patients are randomized into two groups, A. OCT Arm and B. Control Arm

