#### Case Number Estimation:

N=200 patients will be included in the study (100 in each arm).

According to published literature, the average number of MMS stages per lesion is in the range 1.5 to 1.7 [6]. Previous studies with small numbers of patients in non-RCT conditions indicate that presurgical margin mapping with OCT reduces the average number of stages to approximately 1.2 [1-5]. Analysis by a qualified statistician has shown that assuming the true value is 1.2, then 83 patients in the OCT arm will be sufficient to show that the average number of MMS stages is  $< 1.4$  with a confidence level of 95% ( $P < 0.025$ ). This study will be performed with 100 patients in each arm in order to exceed this criterion and show that OCT mapping improves on standard MMS with 1.5 – 1.7 stages.

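### The promised comparison with standard MMS is left as two crude arm means, and the baseline lesion area already recorded for every patient is not used in it; using it would bring a modest gain in precision at no cost in data

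*Protocol*

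**What the plan says.** The formal primary objective (Protocol, Objectives) concerns the OCT arm alone: "Show that the average number of MMS stages by using pre-surgical margin mapping with OCT is" below 1.4. Two other sections go further. Study Design states: "This RCT is designed to quantify the improvement in efficiency" and adds that greater efficiency than standard MMS is to be validated. Case Number Estimation sets 100 patients per arm, partly to "show that OCT mapping improves on standard MMS".

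The stage analysis is in Data and Analysis, section 1: "The average number of MMS stages will be calculated for each arm by dividing the total number of MMS stages for all the patients", with 95% limits for each arm. No between-arm difference, interval or test is given there.

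Under Initial Steps in the Outline Protocol, Observer #1 maps each tumour with OCT before randomisation: "The time taken, size and shape of the mapped border is recorded". Study Design says this applies to all tumours, and Avoiding Bias says this observer does not know the future arm. Section 2 of Data and Analysis uses the resulting area only in comparisons of mapped and excised size. Anatomical location appears in section 3, for OCT-arm lesions that needed more than one stage. The randomisation step names no stratification factor.

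**The concern.** Larger lesions may need more stages. If so, part of the variation in stages could be explained by a measurement that is planned for everyone, taken before randomisation and blind to arm. Two crude means leave that information unused exactly where the protocol wants to quantify the gain over standard MMS. At stake are the width of the interval for that gain and how far it reflects the particular mix of lesion sizes in each arm. Choosing the covariate in advance also avoids a choice made after the results are seen.

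**Working it through.** **1. The protocol's own figure.** Case Number Estimation states: "Analysis by a qualified statistician has shown that assuming the true value is 1.2, then 83 patients in the OCT arm will be sufficient". It gives neither a standard deviation (SD) nor a power, so 83 cannot be derived from its inputs alone. With n = ((1.96 + z_power) × SD / 0.2)², solving back from 83 gives SD = 0.2 × √83 / (1.96 + z_power):

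- 50% power: 1.822 / 1.960 = 0.93
- 80% power: 1.822 / 2.802 = 0.65
- 90% power: 1.822 / 3.242 = 0.56

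A Poisson model for the stages beyond the first (0.4 against 0.2) with 90% power gives (1.96√0.4 + 1.282√0.2)² / 0.2² = 82.2, hence 83. That model and that power are assumptions. The calculation concerns the OCT arm against 1.4 only.

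**2. Crude between-arm comparison.** The protocol expects 1.5 to 1.7 stages under standard MMS and 1.2 with OCT, a difference of 0.3 to 0.5. With 100 per arm, SE = SD × √(2/100). Two-sided 5% power:

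| SD (assumed) | SE | Power, difference 0.3 | Power, difference 0.5 |
|---|---|---|---|
| 0.56 | 0.079 | 96.6% | above 99% |
| 0.65 | 0.092 | 90.4% | above 99% |
| 0.93 | 0.132 | 62.6% | 96.7% |

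**3. Gain from adjustment, by simulation.** Assumptions: 100 per arm; means 1.2 and 1.6; stages = 1 + Poisson; log area with SD 0.8; a binary site group; the same log-rate effect (0.3, 0.5 or 0.7) for log area and for site. None of these effects is in the documents. Interval narrowing is 1 − √(1 − variance reduction).

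| Effect | Variance reduction, area + site | Interval narrower by |
|---|---|---|
| 0.3 | 2.8% | 1.4% |
| 0.5 | 7.3% | 3.7% |
| 0.7 | 12.6% | 6.5% |

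In patients, 200 × (1/(1 − 0.028) − 1) = 6 and 200 × (1/(1 − 0.126) − 1) = 29. Crude and adjusted estimates both average −0.40, so neither is biased. A repeat with a 50% site split and 20,000 trials per scenario gave 1.8%, 7.0% and 13.2% for area plus site. For area alone it gave 1.4%, 5.5% and 10.0%, that is, intervals 0.7%, 2.8% and 5.1% narrower. Crude power in these scenarios was already about 99%.

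**4. Wider sensitivity.** If baseline covariates explain a share R² of the stage variance, the interval narrows by 1 − √(1 − R²): 2.5%, 5.1%, 10.6% and 16.3% at R² = 0.05, 0.10, 0.20 and 0.30. For a difference of 0.3 and SD 0.65, power moves from 90.4% to between 91.7% and 97.4%. At SD 0.93 it moves from 62.6% to at most 77.8%.

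**5. Chance imbalance in area.** The standardised difference between arms has SD √(2/100) = 0.141, so 95% of randomisations fall within ±0.28. The matching shift in the crude difference is 0.277 × √R² × SD. At SD 0.65 this is 0.04 stages (R² = 0.05) to 0.10 stages (R² = 0.30), against an expected 0.3 to 0.5. The crude standard error already includes this variation.

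**The case against.** The strongest reply is that covariates and models are usual content of a statistical analysis plan, which is not shown, and that the protocol does not say crude means are the only analysis. That stands against calling this an omission. It does not remove the point, because the protocol states a specific calculation for stages and also promises a comparison that this calculation does not deliver.

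Three further replies stand in full. The primary objective is a one-sample statement about the OCT arm, which adjustment between arms does not serve. The gain depends on effects that the documents do not report; the protocol itself treats anatomical location as an open question, and excluding lesions above 6 cm² limits the spread in size. And crude power is already high in most of the scenarios above; the exception is a difference of 0.3 with SD 0.93, the value implied by only 50% power.

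A reader might infer that the crude comparison is unprotected from chance imbalance or biased, or that the lack of a named stratification factor is a flaw. The documents support neither: patients are randomised, so the crude difference is unbiased and its standard error covers imbalance, and stratification details are commonly held elsewhere. A reader might also infer that site is available for everyone. Section 3 of Data and Analysis calls for it only in OCT-arm lesions with more than one stage; of the two, only area is shown to be recorded in both arms.

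**Conclusion.** The point holds as a low-cost improvement, not as an error that threatens the trial. The protocol promises a gain over standard MMS, fixes crude arm means without a between-arm difference, and leaves a blinded baseline area out of that analysis. The missing difference with its interval is the larger part of the gap; adjustment is a refinement of it. Under the assumed effects, intervals would be about 1% to 7% narrower with area and site, about 1% to 5% with area alone, and no narrower if area is unrelated to stages. The adjusted estimate would also be balanced on lesion size. It would be wrong to conclude that the result against 1.4 is compromised or that a conclusion is likely to change.

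**What to change.** Add to Data and Analysis, section 1: 'The between-arm difference in mean number of stages will be estimated with a 95% confidence interval by linear regression of number of stages on arm and log Observer #1 OCT area, with robust standard errors; crude arm means are reported alongside.'

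Anatomical site, using the section 3 categories suitably grouped, may be added as a covariate provided it is recorded for all patients in both arms; the grouping should be named in advance. The OCT-arm mean against 1.4 stays unchanged as the primary objective.

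The cost is analysis wording only for area, since the measurement is already planned. Adding site needs one recorded item per patient. No patient or procedure is added. The wording should be settled before stage results are seen by arm.

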## Hypothesis:

That presurgical margin mapping of BCCs with OCT results in a reduction of the number of MMS surgery stages to < 1.4 without adversely impacting clinical outcome.

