#### Population:

##### Inclusion criteria:

- 200 patients with biopsy-proven BCCs who have been referred for MMS
- Adults  $> 18$  years of age
- Informed consent

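### Does dividing total Mohs stages by patients, when the benchmark is per lesion, bias the primary mean against 1.4?

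*Protocol*

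**What the plan says.** Under Data and Analysis, 1. Primary Objective, the mean for each arm is obtained by "dividing the total number of MMS stages for all the patients in the arm, by the number of patients in the arm", with a 95% interval for each arm. The criterion, in the Hypothesis section, is that OCT mapping "results in a reduction of the number of MMS surgery stages to < 1.4", with no unit attached.

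Case Number Estimation gives the comparator in another unit: "the average number of MMS stages per lesion is in the range 1.5 to 1.7". The same paragraph then sizes the trial in patients: "assuming the true value is 1.2, then 83 patients in the OCT arm will be sufficient", against 1.4, "with a confidence level of 95" per cent, with 100 patients per arm planned.

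The Inclusion criteria read "200 patients with biopsy-proven BCCs who have been referred for MMS"; no criterion restricts a patient to one lesion. In Figure 1, Initial Steps, the first mapping is followed by a gap: "The OCT marks are removed and the patient is asked to return at a later date for the surgical procedure". Randomisation is listed next, ahead of the surgical steps. Termination Criteria says that a patient who asks to leave is excluded from the study.

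**The concern.** The primary ratio has patients in its denominator, its benchmark has lesions, and the secondary and tertiary analyses also speak of lesions. Two mechanisms could then separate the ratio from the quantity of interest, which is stages per operated lesion.

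- **Upward.** A patient with two tumours, each cleared in one stage, would add 2 stages over 1 patient. A perfect result would score worse than 1.4.
- **Downward.** A patient randomised but never operated on could stay in the denominator and add nothing to the numerator, although no operated lesion can take fewer than one stage.

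The assumed mean lies only 0.2 below the threshold, so a modest shift could decide the trial. The downward shift is the more serious, because it favours a false claim of success.

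**Working it through.** **The plan's own figure.** The 83 patients cannot be confirmed, because the protocol states neither an SD nor a power. For a one-sample normal test at one-sided 0.025, n = ((1.96 + z_power) × SD / 0.2)². Setting n = 83 implies an SD of 0.65 at 80% power or 0.56 at 90%. The concern does not dispute the 83. It matters here only because it is a number of patients, set directly against a mean drawn from per-lesion literature.

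**The identity.** Let μ be the mean stages per operated lesion, L the mean lesions per operated patient, and f the share of the arm not operated on but counted as zero. The stated ratio then equals μ × L × (1 − f). It equals μ when L = 1 and f = 0. The protocol gives neither L nor f, so the values below are assumptions.

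| Assumed condition | Calculation | Ratio |
|---|---|---|
| 5% of patients with two lesions, μ = 1.2 | 1.2 × 1.05 | 1.26 |
| 10% with two lesions, μ = 1.2 | 1.2 × 1.10 | 1.32 |
| 16.7% with two lesions, μ = 1.2 | 1.2 × 1.167 | 1.40 |
| 5% unoperated as zeros, μ = 1.4 | 1.4 × 0.95 | 1.33 |
| 10% unoperated as zeros, μ = 1.4 | 1.4 × 0.90 | 1.26 |
| 10% unoperated as zeros, μ = 1.5 | 1.5 × 0.90 | 1.35 |

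**Effect on the conclusion, if the conditions held.** The simulations used 20,000 trials with 100 patients in the arm. Success meant an upper 95% t limit below 1.4.

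- *Two-lesion patients, μ = 1.2.* With stages drawn as 1 + Poisson, the chance of success is 97% with one lesion each, 72% at L = 1.05 and 31% at L = 1.10. With two other assumed distributions (a 1-to-4-stage mix with mean 1.195, and a geometric with mean 1.2) it is 86% and 94% at L = 1, 58% and 67% at L = 1.05, and 28% and 29% at L = 1.10.
- *Unoperated patients as zeros, μ = 1.4, 1 + Poisson.* The chance of wrongly showing a mean below 1.4 is 4.0% at f = 0, 20% at f = 5% and 49% at f = 10%.

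**Does the text put L above 1?**

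- Figure 1, Initial Steps and A. OCT Arm, describe mapping one tumour per patient and recording one number of stages.
- Final Observations records one histological subtype, in the singular, and Study-related interventions likewise measures a single lesion.
- No step describes a second lesion, randomisation by lesion, or repeated records within a patient.
- The plural in the Inclusion criteria agrees with the 200 patients and does not show several tumours in one person.
- The plural lesions in the secondary and tertiary analyses are natural, because area, subtype and anatomical site are properties of a lesion.
- Case Number Estimation passes from a per-lesion range to a number of patients without conversion, which makes sense only if the two are one to one.

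**Does the text put f above 0?** No sentence assigns zero stages to an unoperated patient. The stage count in the OCT Arm is recorded at the surgical step, so a patient who never reaches it has a missing value. Those who withdraw on request are excluded under Termination Criteria. Since a true count is at least 1, any zero in the data would show itself at once.

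**The case for a change.** The strongest case for a change is that the protocol states the denominator explicitly. An analysis plan that followed it to the letter would inherit the mismatch, so this is more than a detail left for later. No sentence limits a patient to one lesion or says which lesion would count. The exclusion on request does not mention the denominator and does not cover non-attendance or other reasons for no surgery. A sentence or two would settle all of this, and the simulations show that even a 5% share could matter.

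Much of this is true as far as it goes. The unit wording does differ, the one-lesion rule is implied and not written, and non-attendance is not addressed. It still does not amount to an error in the plan. Reading several lesions into the ratio goes against the singular wording of every procedural step. Reading zeros into it requires a rule that the protocol does not contain. How to treat randomised patients without an outcome is a question of analysis sets, which a protocol commonly leaves to the analysis plan. The simulated losses depend on shares that were chosen and not observed. Even the starting chance of success varies from 86% to 97% with the assumed distribution. The upward mechanism, moreover, could only cost power in the comparison with 1.4; it could not create a false success.

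**Conclusion.** No change is needed. With one operated lesion per patient, which is the natural reading of the procedures, L = 1 and f = 0, stages per patient and stages per lesion are the same number, and the bias is zero. The shifts of 0.06 to 0.20 upward and 0.07 to 0.15 downward in the table are correct arithmetic on assumed shares. The documents do not allow the size or even the net direction of any real shift to be estimated.

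The conclusion rests on two assumptions: that each patient enters with a single study lesion, and that the mean is taken over patients who had Mohs surgery, with the others reported separately. Both are what a competent analyst would do with this text. The difference in wording between the primary formula and the literature benchmark is a gap filled by ordinary practice.

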#### Secondary Objectives:

- Validate that the reduction in MMS stages by use of OCT mapping does not result in an increase in the size of the surgical defect
- Show that the average time taken to perform OCT margin mapping is  $< 5$  minutes for lesions of area  $< 2 \text{ cm}^2$

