##### A. OCT Arm

5. Observer #2 (the Mohs surgeon) maps the extent of the BCC tumour using OCT. The time taken, size and shape of the mapped border is recorded.
6. The Mohs surgeon performs Mohs surgery using the marked OCT mapped borders as the first stage estimate. The number of MMS stages is recorded.

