##### B. Control Arm

7. Standard Mohs surgery is performed, using clinical assessment for the first MMS stages

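### The trial is randomised to show OCT mapping beats standard MMS, but its primary objective and sizing test only the OCT-arm mean against a fixed 1.4

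*Protocol*

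**What the plan says.** **Comparative aim.** The protocol's Study Design section states: "This RCT is designed to quantify the improvement in efficiency, and validate that it is more efficient than standard MMS". It describes what has not yet been quantified as "the efficiency of the technique, in terms of the reduction in MMS stages versus the additional time required to OCT map the lesion". Case Number Estimation adds that 100 patients per arm will let the trial show an improvement on standard MMS. The first secondary objective takes a reduction as given, asking to validate that "the reduction in MMS stages by use of OCT mapping does not result in an increase in the size of the surgical defect".

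**One-arm criterion.** The Hypothesis is that OCT mapping "results in a reduction of the number of MMS surgery stages to < 1.4". The Primary Objective is worded the same way: "Show that the average number of MMS stages by using pre-surgical margin mapping with OCT is" below 1.4. In Case Number Estimation, 83 patients in the OCT arm suffice to show a mean below 1.4 if the true mean is 1.2, with 95% confidence (P < 0.025). Standard MMS enters only as a published range of 1.5 to 1.7.

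**Analysis.** Data and Analysis, 1. Primary Objective, gives the mean number of stages in each arm, followed by: "The 95% confidence levels for each arm will be calculated". It mentions no difference between arms.

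**Procedures.** In Figure 1, step 6 (OCT arm) ends "The number of MMS stages is recorded". Step 7 (control arm) reads only "Standard Mohs surgery is performed, using clinical assessment for the first MMS stages".

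**The concern.** A claim of being better than standard MMS is a claim about a difference between two arms. A criterion that compares one arm with a constant supports it only if standard MMS in this trial behaves as the literature says. The protocol pays for a randomised control arm, which would remove that dependence, and then leaves it out of the hypothesis, the primary objective and the sizing.

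This could mislead in two directions. If local control results are at the high end of the published range, a worthwhile reduction could be reported as a missed objective. If they are better than the published range, the objective could be met although OCT mapping did nothing. Choosing a between-arm comparison after the stage counts are known would be post hoc.

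**Working it through.** **Inputs from Case Number Estimation.** OCT mean 1.2; benchmark 1.4; one-sided 0.025; 83 patients sized, 100 per arm planned; control mean 1.5 to 1.7 from the literature. SD and power are not given, so every SD below is an assumption.

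**1. The protocol's 83.** The one-sample formula is n = (SD × (1.96 + z_power) / 0.2)². Solving for SD with n = 83 gives SD = 0.2 × √83 / (1.96 + z_power):
- 90% power: 1.822 / 3.242 = 0.56
- 80% power: 1.822 / 2.802 = 0.65
- 50% power: 1.822 / 1.960 = 0.93

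The exact t version gives 0.555, 0.643 and 0.919, used below. The 50% case is an extreme. A model of one stage plus a Poisson number of extra stages also gives 83 at 90% power: ((1.96 × √0.4 + 1.2816 × √0.2) / 0.2)² = 9.064² = 82.15, rounded up. Each of these routes to 83 is a one-arm calculation against 1.4.

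**2. What the criterion demands.** I read it as the upper 95% limit for the OCT arm lying below 1.4. With n = 100 and SD 0.643 the observed mean must be below 1.4 − 1.984 × 0.643 / 10 = 1.27, whatever the control arm shows.

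**3. Chance of meeting the criterion, against between-arm power.** 100 per arm. The criterion column is the non-central t probability for the OCT arm. The between-arm column is a two-sided 0.05 t test with a common SD. Entries are for SD 0.555 / 0.643 / 0.919.

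| True means (OCT, control) | Criterion met | Between-arm power |
|---|---|---|
| 1.2, 1.5 | 95% / 87% / 58% | 97% / 91% / 63% |
| 1.35, 1.7 | 14% / 12% / 8% | 99% / 97% / 76% |
| 1.4, 1.7 | 2.5% each | 97% / 91% / 63% |
| 1.5, 1.5 (no effect) | 0.01% / 0.02% / 0.12% | – |
| 1.3, 1.3 (no effect) | 43% / 34% / 19% | – |
| 1.2, 1.2 (no effect) | 95% / 87% / 58% | – |

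**4. Variance rising with the mean.** Simulated stage counts (20,000 trials, unequal-variance t):

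| True means (OCT, control) | Model | Criterion met | Between-arm power |
|---|---|---|---|
| 1.2, 1.5 | 1 + Poisson | 97% | 96% |
| 1.2, 1.5 | geometric | 94% | 88% |
| 1.4, 1.7 | 1 + Poisson | 4% | 82% |
| 1.4, 1.7 | geometric | 5% | 63% |

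With unequal SDs of 0.64 (OCT) and 0.85 (control), between-arm power for 1.2 against 1.5 is 80%.

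**5. Is 100 per arm enough for the comparison?** For a difference of 0.30, the largest common SD is 0.65 for 90% power and 0.75 for 80%. Check of the first: 0.65 × √(2/100) = 0.092, and 0.30 / 0.092 = 3.26, close to the 3.24 required.

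**The case against.** **A SAP may supply the contrast.** Both arms are summarised, the comparison is stated as intended, and a protocol often leaves the test to the SAP. So the lack of a named test would not by itself be a finding. But the hypothesis, the primary objective and the sizing basis are fixed in this protocol, and they do not match its stated aim. Two separate intervals are not an interval for the difference.

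**The success rule is an inference.** No sentence says the trial succeeds if the upper limit is below 1.4. That is correct. The reading combines the primary objective, the P < 0.025 in the sizing and the per-arm intervals. No other reading brings the control arm into the primary objective.

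**Little harm under the protocol's own premise.** This stands in part. With control at 1.5 to 1.7, meeting 1.4 does imply improvement: false success is at most 0.12% in the t calculations and about 0.3% in the count models. No section suggests a control mean as low as 1.2 or 1.3. The opposite error needs no such departure, since 1.7 lies inside the published range.

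**The 1.7 to 1.4 example sits on the null.** Fair: there, 2.5% is simply the type I error of the stated objective. The 1.7 to 1.35 example avoids this and carries the argument.

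**The comparison can have less power at the design point.** True for 1.2 against 1.5 in three scenarios: 96% against 97%, 88% against 94%, and 80% against 87% (unequal SDs). This is a real cost and belongs in the decision.

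**Step 7 is editorial.** Agreed; the analysis section already requires control-arm counts.

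**Conclusion.** The mismatch is real and should be corrected. As written, neither meeting nor missing 1.4 answers the question the trial was randomised to answer, because the control arm cannot alter the primary result.

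The larger practical risk is a missed benefit: for a true reduction from 1.7 to 1.35, an 8% to 14% chance of meeting the criterion against 76% to 99% power for a between-arm test. False success matters only if local control averages fall below 1.4, which the protocol gives no reason to expect but which the concurrent control arm exists to rule out.

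The percentages rest on assumed SDs of 0.56 to 0.92. The textual contradiction does not depend on them. The sample size is probably adequate for the comparison, so the fault lies in the objective more than in N.

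**What to change.** - **Hypothesis and Primary Objective:** state the primary question as the OCT-minus-control difference in mean number of MMS stages.
- **Data and Analysis, 1. Primary Objective:** add that this difference will be calculated with a two-sided 95% confidence interval and tested at 0.05 as the primary analysis. Keep the per-arm means and intervals, and keep an OCT mean below 1.4 as a supporting criterion.
- **Case Number Estimation:** restate the sample size for the comparison, giving the sponsor's own SD for each arm and the power. The back-solved SDs here are no substitute.
- **Figure 1, step 7:** say that the number of stages is recorded, as step 6 does.
- **Optional:** adjust for the OCT area mapped by Observer #1 before randomisation, to gain precision.

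The stage difference covers only one side of the protocol's notion of efficiency; the mapping time, already collected, should be reported beside it. Limiting the aim to the 1.4 benchmark would also restore consistency, but it would give up the comparison that the control arm was included to provide.

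**Cost.** Wording in five places and no new measurement. No extra patients are needed for 1.2 against 1.5 if the common SD is at most about 0.65 (90% power) or 0.75 (80%). With a larger SD and control at only 1.5, power falls, to 63% at SD 0.92, and the sponsor would have to accept that or enlarge the trial. The change should be made before stage counts are compared.
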